## *Acronym*

CALIBREX

## *Objectives*

**Aim 1:** Investigate the effect of candesartan compared to lisinopril on the progression of cognitive function evaluated by a battery of neuropsychological tests assessing executive function, memory, attention and cognitive speed in hypertensive older adults with executive mild cognitive impairment.

**Aim 2:** Investigate the effect of candesartan compared to lisinopril on cerebral perfusion, cerebrovascular reserve (vasoreactivity to carbon dioxide) assessed by arterial spin labeling MRI and microvascular brain injury reflected by diffusion tensor imaging measures of connectivity.

**Aim 3:** Identify underlying mechanisms explaining the effects of candesartan on neuroimaging (AIM 3A) and cognitive (AIM 3B) outcomes relative to lisinopril including effects on arterial stiffness, atherosclerosis (carotid intima-media thickness, CIMT), and vascular inflammatory and endothelial markers.

## *Design and Outcomes*

Our overall aim is to conduct a 1-year double blind randomized control trial comparing candesartan to lisinopril in individuals with hypertension and executive mild cognitive impairment. Our measures include cognitive function, cerebral perfusion and reserve, markers of vascular brain damage, atherosclerosis, arterial stiffness, vascular inflammation and endothelial function.

## *Interventions and Duration*

The intervention includes candesartan or lisinopril with add-on antihypertensive medications to achieve blood pressure control to below 140/90 mm Hg. The duration of the study is 1 year.

## *Sample Size and Population*

Our target sample size is 140. To achieve this sample size, **160** individuals will be enrolled to account for drop-outs. Individuals will be recruited from the greater Atlanta area to achieve a final sample of 140 (70 in candesartan group, 70 in lisinopril group). Our target population is subjects: 60 years or older, blood pressure (BP) >140/90 mm Hg or receiving antihypertensive medications, with executive MCI.

## 1. STUDY OBJECTIVES

Our overall aim is to conduct a 1-year double blind randomized control trial comparing candesartan to lisinopril in 140 individuals with hypertension and executive mild cognitive impairment. Our specific aims are:

**Aim 1:** Investigate the effect of candesartan compared to lisinopril on the progression of cognitive function evaluated by a battery of neuropsychological tests assessing executive function, memory, attention and cognitive speed in hypertensive older adults with executive mild cognitive impairment.

**Hypothesis 1:** Candesartan is associated with less decline in executive function compared to lisinopril.

**Aim 2:** Investigate the effect of candesartan compared to lisinopril on cerebral perfusion, cerebrovascular reserve (vasoreactivity to carbon dioxide) assessed by arterial spin labeling MRI and microvascular brain injury reflected by diffusion tensor imaging measures of connectivity.

**Hypothesis 2:** Candesartan is associated with less decline in cerebral perfusion, vasoreactivity to carbon dioxide, and evidence of microvascular brain injury (white matter integrity) compared to lisinopril.

**Aim 3:** Identify underlying mechanisms explaining the effects of candesartan on neuroimaging (AIM 3A) and cognitive (AIM 3B) outcomes relative to lisinopril including effects on arterial stiffness, atherosclerosis (carotid intima-media thickness, CIMT), and vascular inflammatory and endothelial markers.

**Hypotheses 3:** Relative to lisinopril, treatment with candesartan is associated with lower CIMT, arterial stiffness, and inflammatory and endothelial function markers at 12 months, which in turn are associated with improved cerebral perfusion, vasoreactivity, and white matter integrity measures (Hypotheses 3A) as well as less decline in executive function (Hypotheses 3B) at 12 months.

## 2. BACKGROUND AND RATIONALE

### 2.1 Background

**1- Hypertension and executive function:** It is estimated that nearly 30% of older adults and 50% of older hypertensives have executive dysfunction, which is generally undetected. Executive function refers to cognitive operations that control and coordinate planning and performing complex tasks. It can be viewed as the composite of subdomains including set shifting, working memory, fluency, and processing speed. It reflects the functioning of a broad network of neural structures, with particular involvement of the dorsolateral prefrontal cortex. This brain region and its white matter connections are highly susceptible to vascular injury. Executive dysfunction without dementia belongs to a larger construct of cognitive disorders in the context of vascular brain injury. Multiple terms have been suggested for this pattern including non-amnesic mild cognitive impairment (MCI), executive MCI or mild vascular cognitive impairment (VCI). To date, few clinical trials have focused on this group. Beyond lowering blood pressure and reducing the risk for stroke, the effectiveness of antihypertensives in reducing the progression of executive dysfunction remains unknown. The significance of studying the effect of antihypertensive therapy on executive function is based on these observations: only hypertensives with executive dysfunction, rather than memory decline, progressed to dementia; hypertensive individuals with executive dysfunction have similar mortality to those with dementia; and, as we have demonstrated in a previous report, hypertension with executive dysfunction has higher mortality than hypertension alone.

**2- ACEI vs ARB in the brain:** There is a brain renin angiotensin system (RAS) that potentially links hypertension to cognitive function. In the brain, Angiotensin II (Ang II) binds 2 main receptors, among others, AT1 and AT2 which have opposing effects. AT1 activation leads to vasoconstriction, endothelial dysfunction and smooth muscle hypertrophy. In animals, AT2 activation decreases infarct area after an ischemic injury by increasing cerebral perfusion in the penumbra, decreases superoxide production, activates neuronal repair systems by promoting neuronal cell differentiation and neurite growth, and decreases inflammation and axonal degeneration. AT2 receptors are distributed in the cerebrovascular wall

and in the thalamus, hypothalamus and brain stem among other locations and AT2 activation may positively affect cognition. ACEIs decrease Ang II production and hence decrease activation of both receptors whereas ARBs block AT1 but not AT2. ARBs also increase Ang II and possibly up-regulate AT2. This selective blockade of AT1 and possible hyperstimulation of AT2 may provide superior and brain-specific beneficial effects compared to ACEI. Based on this AT2-hypothesis, we are suggesting that ARBs have superior effects relative to ACEIs in executive and cerebrovascular function. In the largest observational study to date, use of ARBs was associated with lower risk of dementia and Alzheimer's disease (AD) compared to ACEI and other antihypertensives. In our pilot study, candesartan was superior to lisinopril in preserving executive function.

*3- Cerebral perfusion in hypertension and executive MCI:* Adequate cerebral perfusion is important for cognitive performance and hypertension is associated with declines in cerebral perfusion and cerebrovascular reserve. Our recent work has shown that hypertensives have significantly decreased perfusion and reserve assessed by ASL-MRI. Decline in perfusion is associated with executive dysfunction. In our pilot study, we found that decreased cerebrovascular reserve, assessed by measuring the change in cerebral blood flow in response to carbon dioxide (CO2), is associated with decreased executive function (see prelim data). Other studies suggest a decrease in CO2 vasoreactivity in patients with dementia. Recent work by our collaborator's team suggests that executive MCI patients demonstrate hypoperfusion in the middle frontal cortex and precuneus. RAS is involved in cerebral perfusion regulation. We recently reported that genetic polymorphisms in RAS are associated with cerebrovascular reserve, and others found an association of RAS genetic polymorphisms with vascular brain injury. In animal studies, activation of AT2 improved cerebral perfusion and ARBs improved cerebral perfusion and ameliorated ischemic changes from atherosclerosis and hypoperfusion. Since ACEI and ARB have differential effect on AT1 and AT2, we hypothesize that ARBs will be superior to ACEI in their effects on cerebral perfusion and reserve. Our preliminary data suggest that ARB use may be associated with improved cerebral blood flow velocity compared to ACEI.

*4. White matter integrity and executive function:* Hypertension and executive impairment are also associated with microvascular brain disease in similar overlapping regions and tracts (frontal and subcortical regions) notably presenting as white matter hyperintensities (WMH) on MRI or with loss of white matter integrity on diffusion tensor imaging (DTI) even in normally appearing white matter. DTI-based indices of white matter integrity are very sensitive early indicators of vascular damage in the aging brain. DTI also provides high sensitivity to detect white matter change over a period of 12 months. New preliminary work by our team suggests that hypertension is associated with decreased Fractional Anisotropy in the frontal lobe. More recently, Diffusion Tensor Tractography (DTT) has been used to visualize and quantify integrity in specific brain networks and tracts. Executive dysfunction is associated with loss of integrity in the left anterior cingulate tract and precuneus. The effect of antihypertensive therapy on white matter integrity has not been studied. Since AT2 activation is associated with axonal regeneration and improved neuronal repair, ARBs may have superior effects on white matter integrity measures.

*5. Mechanistic approach for the effect of ARBs on the brain:* To further support our AT2 hypothesis in the brain, we will measure processes that are likely to be affected by AT2. AT2 activation is associated with decreases in vascular remodeling and inflammation and restores endothelial dysfunction by improving NO homeostasis. Increased vascular stiffness and atherosclerosis reflected by higher carotid intima-media thickness (CIMT) contributes to vascular brain injury and cognitive impairment. AT1 activation leads to greater atherosclerosis and vascular stiffness and ARBs, more so than ACEIs, lower CIMT and arterial stiffness. In the cerebral arteries, candesartan resulted in the normalization of mean media thickness, leading to decreased arterial stiffness. ARBs also lower inflammatory markers, more so than ACEI, and restore proper endothelial function possibly via AT2 hyperstimulation. Inflammation also impairs endothelial function and increases atherosclerosis. Recent evidence suggests that proper endothelial function requires the replacement of dysfunctional cells and that endothelial progenitor cells (EPC) function as a reservoir for newer endothelial cells. The number of EPC has been linked with arterial stiffness, atherosclerosis, vascular brain injury and dementia. ARBs may improve the proliferation and function of EPCs in hypertension via an antioxidant effect. Therefore the potential mechanisms by which ARBs may prove to be superior to ACEIs in the brain may be related to their effects on atherosclerosis, vascular stiffness, inflammation, and optimal endothelial function and turnover. This project will test these hypotheses.

## 2.2 Study Rationale

[figure not shown]
Selective blockade of AT1 (ARB) vs dual blockade of AT1 and AT2 (ACEI) allows testing the AT2-hypothesis. We suggest that the non-inhibition of AT2, AT2 up-regulation and increased Ang II that results from ARB treatment would explain this superior effect. AT1 and AT2 have opposing effects on endothelial function, inflammation, and vascular stiffness, which in turn are associated with perfusion, cerebrovascular reserve (CO2 vasoreactivity), white matter connectivity and executive function. We will be able to test these hypotheses by comparing the effect of ACEI and ARB on executive function (AIM1), cerebrovascular function and white matter connectivity (AIM2), and investigate underlying vascular, endothelial, and inflammatory mediators (AIM3).

## 2.3 Prior Studies

### 1- Safety and blood pressure trajectory of short-term withdrawal of antihypertensive medications in older adults:

The short-term safety of, and blood pressure changes after withdrawing hypertension treatment in older adults in preparation for clinical trials have not been well established. Participants were enrolled in a clinical trial and antihypertensive medications were tapered over three weeks (week 1: reduction by 25-50%, week 2: 50-75%, week 3: off). Blood pressure was measured at the initial visit and after stopping all antihypertensive therapy (personnel) and twice a day during the taper phase (provided monitor). Trend analyses and linear models were used to assess changes in blood pressure. All participants (n=53, mean age=71 years, total of 1158 readings) successfully tapered their medications with no symptoms. Only 2% of the readings exceeded 180/100 mm Hg but none were consecutive. Blood pressure gradually increased with an overall increase of 12/6 mm Hg, 95% confidence interval (CI) [4/1,21/11]. The daily increase in blood pressure was 0.2 mm Hg (SE=0.1) in both the systolic and diastolic blood pressure. Increases in systolic and diastolic blood pressure were comparable for all antihypertensive classes (p>0.05 for all). Blood pressure changes are displayed in **Figure 1**. Short-term (<3-4 weeks) withdrawal of antihypertensive therapy in older adults with hypertension is safe and is associated with mild increases in blood pressure.

**Figure 1: Trajectory of daily blood pressure over time in the study participants. Solid lines are the mean blood pressure at each day and dotted lines are the 95% confidence interval**

## 3. STUDY DESIGN

This is a double-blind randomized clinical trial in individuals with hypertension and executive MCI without dementia. Participants will be treated for 1-year with candesartan or lisinopril. Additional antihypertensives will be added to achieve blood pressure control to below 140/90 mm Hg in both groups. Our study will recruit 160 participants to achieve a sample size of 140 with 70 participants in each group. Our outcome measures include cognitive function, cerebral perfusion and reserve, markers of vascular brain damage, atherosclerosis, stiffness, vascular inflammation and endothelial function.

## 4. SELECTION AND ENROLLMENT OF PARTICIPANTS

### 4.1. Inclusion Criteria

- (1) Age: 60 years or older;
- (2) Hypertension: SBP $\geq$ 140 mm Hg or DBP $\geq$  90 mm or receiving antihypertensive medications. Currently treated hypertensive individuals are eligible if they are willing to taper their medications. We will use a step-wise protocol of lowering antihypertensive medications;
- (3) Executive MCI will be defined using these criteria:

- (a) The Montreal Cognitive Assessment (MoCA) score less than or equal to 26: MoCA is a 30-point scale administered in 10 minutes, is validated in multiple languages and is highly sensitive to identify mild vascular-related cognitive dysfunction (sensitivity 90% and specificity 87%).
- (b) Executive dysfunction: A performance at the 10th percentile or below on at least one of four screening tests for executive function: Trail Making Test, Part B (TMT-B), modified Stroop interference, Digit Span and Digit Sequencing, and Letter fluency
- (c) Minimal Functional limitation as reflected by the Functional Assessment Questionnaire (FAQ)  $\leq 7$ .

## 4.2 Exclusion Criteria

- (1) Intolerance to candesartan or lisinopril ;
- (2) SBP >200 or DBP >110 mm Hg;
- (3) Renal disease or hyperkalemia (SCr >1.99 mg/dl or K > 5.5 meq/dl);
- (4) Active medical or psychiatric problems (An active problem is one that requires medical attention and is deemed as a safety risk by the study physician, for example current cancer treatment, infections such as pneumonia, current gastrointestinal or other internal bleeding, HIV treatment, hematological disease, Parkinson's disease, multiple sclerosis)
- (5) Uncontrolled congestive heart failure [shortness of breath at rest or evidence of pulmonary edema on exam];
- (6) History of stroke in the past 3 years (self-reported clinical stroke within the past 3 years/ incidental infarcts on MRI scanning is allowed);
- (7) Inability to perform the study procedures (those with contraindications for MRI will be enrolled but will not undergo the MRI; those with history of asthma, COPD, or significant pulmonary disease will not undergo the CO2-reactivity protocol);
- (8) Women of childbearing potential
- (9) Current use of acetylcholine-esterase inhibitors or NMDA receptor antagonist (memantine) or a diagnosis of dementia self-report or care-giver report
- (10) In those who lack decision capacity, a *study surrogate* who can sign on their behalf will be required. Since we are enrolling only those with MCI, we anticipate that most participants will have decision capacity
- (11) Current use of Lithium, as most antihypertensive classes may lead to increased lithium toxic levels.

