## 7.2 Description of Evaluations

7.2.1 Screening: Initial eligibility will be determined via phone interview.. This screening process will determine the specific inclusion and exclusion criteria that can be evaluated by self-report, including age, hypertension or blood pressure diagnosis, and prior medical issues detailed in the inclusion/exclusion criteria. Data collected during this interview will be stored de-identified for future data analysis with no links to the patient or their PHI. A study ID number will be used to collect data and will not be linked to the participant. Those who are eligible via phone interview will be invited for a clinic screening visit along with their next-of-kin, if possible. The screening visit will include: explaining study details and obtaining informed consent, cognitive assessment, medical history, current medications, 2 seated blood pressure measurements, and baseline metabolic panel. Eligible participants currently receiving antihypertensive medications who agree to stop antihypertensive medications will be instructed on a taper protocol and asked to return for baseline evaluation and randomization.

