4- A summary of symptoms will be provided to the subjects and/or their proxy. They will be asked to share this information with their spouses or other family members living in the same household or other close caregiver. They will be instructed to call the investigators immediately if any of these symptoms occur to arrange the transfer to the nearest emergency room. They will be provided with a pager number for the investigators. Weekly contact with the subject will be conducted by phone to obtain the blood pressure readings and review of any symptom that occurred.

5- The subjects will be asked to repeat the blood pressure measurement within 60 minutes if the reading is above 180/110 mm HG and call the investigators ( by phone or pager) anytime that they have two consecutive readings exceeding 180 mm Hg systolic or 110 mm Hg diastolic or have any unexpected discomfort, dizziness, or headaches. The study physician will then recommend based on the prior blood pressure readings and the participant symptoms to either alter the way the blood pressure medication is being reduced, take extra dose of the blood pressure medication, or resume all usual doses of all blood pressure medications immediately (the doses before the study) and continue measuring blood pressure as instructed. A failed taper is defined as persistent (>2 consecutive readings on 2 consecutive days) elevation in blood pressure >180/110 mm Hg. In the event that the participant failed the taper, the participant is asked to go back on their usual antihypertensive medications and is withdrawn form the study. The study personnel will contact the subject daily to obtain the blood pressure readings. This will continue until the blood pressure is back to the level before the medication reduction was started and they will be referred to their primary care physician for chronic blood pressure management. For their safety they will not be included in the study.

[figure not shown]

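### Section 4.2(2) sets one systolic ceiling of 200 mm Hg for everyone, so a treated person at 181-200 mm Hg on treatment may start drug withdrawal, although Section 8.3 treats persistent home systolic pressure above 180 as a failed taper

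*Combined protocol and SAP*

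**What the plan says.** **Entry.** Section 4.2(2) excludes "SBP >200 or DBP >110 mm Hg". It does not say whether the reading is on or off treatment, or which reading counts. For treated people, Section 4.1(2) adds one condition: "Currently treated hypertensive individuals are eligible if they are willing to taper their medications". Section 7.2.1 takes "2 seated blood pressure measurements" at the screening visit, before any taper, and then moves straight on: "Eligible participants currently receiving antihypertensive medications who agree to stop antihypertensive medications will be instructed on a taper protocol". No further pressure figure stands between screening and the first dose reduction.

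**Taper.** Section 8.3 lowers doses stepwise, with home readings twice a day and staff contact at least weekly. The participant is to call the investigators after "two consecutive readings exceeding 180 mm Hg systolic or 110 mm Hg diastolic"; one option for the physician is then to restore all usual doses at once. The failure rule reads: "A failed taper is defined as persistent (>2 consecutive readings on 2 consecutive days) elevation in blood pressure >180/110 mm Hg". Usual drugs are then resumed and the person is withdrawn: "For their safety they will not be included in the study". The visit-window table in Section 7.1 limits time fully off drugs to one week.

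**Judgement at entry.** Section 4.2(4) excludes active medical problems, explained as follows: "An active problem is one that requires medical attention and is deemed as a safety risk by the study physician". Section 8.5 names severely elevated pressure at screening as a problem needing medical attention and calls for referral. Neither gives a pressure value.

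**The concern.** A ceiling of 200 may suit someone untreated who is about to start therapy. A treated person at 181-200 is in the opposite position: pressure is already high despite treatment, and that treatment is about to be reduced and stopped. Section 8.1 names the hazard of withdrawal as marked pressure elevation with neurological or cardiac symptoms. The plan itself regards persistent systolic pressure above 180 during the taper as unsafe, yet no written figure stops a taper from starting when office pressure is already above that level. Whether such a person is kept out depends on the physician alone.

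**Working it through.** The protocol states no figure for this point that could be reproduced. The check compares its written limits and follows their timing.

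**1. The limits side by side**

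| | Entry (4.2(2)) | Failed taper (8.3) | Gap |
|---|---|---|---|
| Systolic, mm Hg | excluded if >200 | >180, persistent | 200 - 180 = 20 (readings 181-200) |
| Diastolic, mm Hg | excluded if >110 | >110, persistent | 110 - 110 = 0 |
| Setting | office, two seated readings | home, twice daily | different measures |

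**2. Which safeguards act before the first dose cut**

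- Before: physician judgement under 4.2(4) and referral under 8.5. Read together they allow exclusion, but neither has a number, and 8.5 does not say that the taper is withheld.
- During or after: gradual reduction, home monitoring, the call rule, the failed-taper rule and the one-week limit off drugs.

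**3. How fast the later rules can act**

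- Call rule: two consecutive readings, with a high reading repeated within 60 minutes, so it can be met on the first day of monitoring.
- Failed-taper rule: more than 2 consecutive readings means at least 3. At two scheduled readings a day this spans 2 days.
- Week 1 halves one drug. Counting drugs equally (an assumption), the cut is 0.5/1 = 50% of treatment on one drug, 0.5/2 = 25% on two and 0.5/3 = 17% on three. This describes the first step. It does not measure risk.

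**4. Illustration with the prior withdrawal study (Section 2.3)**

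The mean systolic rise was 12 mm Hg (95% CI 4 to 21). Projected pressure = starting pressure + rise.

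| Rise | From 181 | From 200 | Start that reaches 180 |
|---|---|---|---|
| 4 | 185 | 204 | 180 - 4 = 176 |
| 12 | 193 | 212 | 180 - 12 = 168 |
| 21 | 202 | 221 | 180 - 21 = 159 |

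This assumes that the mean rise holds at high starting pressures and that office and home readings are interchangeable. The protocol shows neither. The interval is for the mean, so it does not give the spread between individuals.

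**5. What the prior study says about this group**

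All 53 participants tapered without symptoms. Of 1158 readings, 2% exceeded 180/100, none of them consecutive. Entry pressures are not reported, so the study does not address people who start at 181-200.

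**The case against.** The strongest reply is that the two limits do different jobs. One is an entry ceiling on office readings; the other is a stopping rule that needs persistence at home. Section 8.2 recognises that pressure can be high at visits and normal or low at home. This stands. A reader might infer that the protocol contradicts itself, or that someone at 181-200 has failed the taper before starting it. The text supports neither.

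A reader might also take the taper table to mean 14 days (one drug) or 28 days (three drugs) of reduced or no treatment, counted to the end of the baseline-visit week. That is the full schedule. A person whose home pressure really stays above 180 should trigger the call rule within a day or so and the failure rule within about two days. People likely to complete the schedule are those without persistent home readings above 180, for whom the worry is weakest. This stands too.

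The entry stage is also not unguarded: 4.2(4) and 8.5 let the physician refuse such a person, and the primary care provider is told before drugs are changed if the participant agrees. The reply falls short here, because these provisions are discretionary and unnumbered, while 4.2(2) as written makes the person eligible.

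Two cautions remain. The participant-flow figure announced in Section 7.1 and a figure after the taper text in Section 8.3 are not shown, so a limit in either could not be seen. And 180 is not derived from the illustration, which points to starting pressures of 159-176. Its merit is that it is the plan's own safety threshold.

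**Conclusion.** The point holds in a limited form. In the text supplied, treated and untreated people share one entry ceiling, and a treated person with an on-treatment office systolic pressure of 181-200 may start withdrawal. The gap is 20 mm Hg systolic and nil diastolic. If the call and failure rules are followed, exposure is probably a matter of days. The number of people affected is not given and is probably small.

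The protocol does not show that harm is likely: its withdrawal experience is reassuring overall but silent on this range. Nor should a reader infer any bias in the trial's result. The taper comes before randomization, so the comparison of candesartan with lisinopril, its power and its error rate are unaffected. This is a modest participant-safety point that merits a written limit. It rests on reading 4.2(2) as covering on-treatment screening pressure and on there being no lower limit in the figures not shown.

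**What to change.** In Section 4.2(2), add that participants who will be tapered are excluded if the mean of the two seated on-treatment screening readings is systolic >180 or diastolic >110 mm Hg. Keep 200/110 for untreated people. Naming the mean settles which reading counts.

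The change is one clause and needs no new measurement. It costs a few more screen failures, including some people whose office readings run above their home readings and who might have tapered without trouble.
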